Paracervical block with IUD insertion versus no paracervical block IRB

NCT02904915

Version Date: 01/04/2017

Paracervical block with IUD insertion versus no paracervical block IRB

Protocol Title:	Paracervical block versus no paracervical block during IUD insertion
Principle Investigator:	[name]
Co-Investigators:	[name]
Population:	50 Adults who present for IUD insertion at several UT Physicians Obstetrics and Gynecology clinics.
Number of sites:	Three: [name] Ross OB/GYN Continuity Clinic: UTPB Suite 350; UT Physicians Women's Center- TMC: UTPB Suite 250; UT Physicians Women's Center- Bellaire: [name]
Study duration:	October 2016 until completion (anticipated 1 year)
Subject duration:	20 minutes or less to place block and insert IUD

General information

We propose to compare paracervical block versus no local analgesia in women who present for IUD insertion. We will compare the patient's procedural pain level with tenaculum placement and IUD insertion using paracervical block versus no analgesia during the IUD insertion procedure..

Background Information

In the United States, approximately 7% of women used intrauterine devices (IUD) for contraception in 2012 (Guttmacher institute). To date, no standard method of pain control with IUD insertion has been proposed or adopted. IUDs have a less than 1% rate of failure depending on the type of IUD used and have a high rate of compliance. Some barriers to women obtaining the IUD are: cost and the perceived pain associate with IUD insertion including stimulation of cervical parasympathetic

and sympathetic nerve fibers and prostaglandin release. Some research has been done on the difference in pain experienced with IUD insertion using paracervical block with conflicting results (Mody, Cirik). In a study of nulliparous women, 2% topical lidocaine gel has been found to be effective for pain relief at the tenaculum site however its use in a clinical setting is uncommon (Rapkin, et al). This study involved self-administration of the topical product prior to the procedure and may be distasteful to some patients. Despite the controversy regarding the effectiveness of various techniques for pain management, a recent revision of the U.S. Select Practice Recommendations for Contraception (2016) includes a recommendation that “paracervical block with lidocaine might reduce patient pain during IUD insertion.”

We are interested in performing an open label randomized controlled trial of local block versus no local block in a group of women who present to the [name] Ross OB/GYN Continuity Clinic, the UT Physicians Women's Center, and the UT Physicians Women's Center- Bellaire for IUD insertion. Individual providers vary in their use of a local block for pain with IUD procedures. We will collect data on the vital signs of each woman undergoing an IUD insertion procedure. We also plan on collecting demographic information on each patient involved in the study. We plan on assessing the pain of each individual throughout each individual IUD insertion procedure using a visual analogue pain scale. Each patient will be randomized to receive either a paracervical block or no local analgesia. A standard protocol for administration of paracervical block will be delineated, distributed, and used for the study. Patient pain will be assessed prior to, during the placement of tenaculum, and after the procedure using the visual analogue scale tool.

The study will take place at the clinics mentioned above. IUD placement will be carried out by residents and faculty at the Memorial Hermann and LBJ Hospital Obstetrics and Gynecology residency programs rotating through the aforementioned clinics.

Objectives

We would like to compare patient pain perception in IUD insertion when using paracervical block versus no block. We aim to improve pain in this patient population.

Study Design

The study will be an open label randomized controlled trial. Each woman will be consented to the study and either randomized to receive paracervical block or routine care (no local analgesia). The level of pain of each woman will be assessed before the procedure but after placement of the speculum, during placement of the tenaculum, and after the procedure by using a visual analogue pain assessment scale. Vital signs will also be taken prior to and after completion of the procedure.

Each patient will be consented prior to the study.

We would like to assess the following in each of the study participants undergoing the IUD insertion procedure.

- a) Age, race, gravity, and parity
- b) Type of IUD received
- c) Randomization status, i.e. whether each participant received a paracervical block or not
- d) History of vaginal, pelvic, or cervical surgery
- e) History of sexually transmitted infection or pelvic inflammatory disease
- f) Vital signs (including but not limited to blood pressure, respiratory rate, pulse, and oxygen saturation) before and after the procedure
- g) Patient rating of pain before, during tenaculum placement, and after the procedure.
- h) Complications associated with IUD insertion procedure or block itself (i.e.: cervical stenosis requiring dilation, failure of IUD placement, bleeding)
- i) Other pain medications taken by the patient on the day of but prior to the procedure

Study Population

Women of reproductive age, having IUD placed at the [name] Ross OB/GYN continuity clinic, The UT Physicians Women's Center, and the UT Physicians Women's Center- Bellaire during the study time.

Inclusion criteria:

Women of reproductive age between ages 18 and 52 who present for an IUD insertion procedure.

Exclusion criteria: Women less than age 18 and greater than age 52, women with current PID, women who are not good candidates for an IUD, and patients who have a Lidocaine allergy.

Women aged 18 and over will undergo a consent process prior to being enrolled in the study.

Study Procedures

Women who meet inclusion criteria who present to the abovementioned locations will be informed of the study, and those agreeing will be asked to sign a consent.

These patients will be informed that routine care for our practice is no analgesia. These women will then be randomized to either a group getting no analgesia during the IUD insertion procedure and those receiving a paracervical block with 1% Lidocaine prior to the procedure. An established protocol will be used for the paracervical block arm of the study. Patient vitals will be assessed 5 minutes prior to procedure and 5 minutes after procedure. Patient pain scale will be assessed after speculum placement but prior to any procedure, with tenaculum placement and after placement of the IUD. All complications associated with the IUD insertion procedure will also be analyzed as will failure to successfully insert the IUD.

The following paracervical block protocol will be used for this study:

Paracervical block protocol (Study arm)

Tools:

Speculum

10 cc syringe

1% Lidocaine

Single tooth tenaculum

1. Obtain consent and randomization
2. Perform pre-procedure vital signs
3. Insert the speculum into the vagina
4. Perform pain scale #1
5. Identify the cervix
6. Apply Betadine to the cervix and surrounding vaginal tissue
7. Insert the syringe into the cervico-vaginal junction at 12 o'clock (the anticipated tenaculum site). Inject 2 cc of Lidocaine at the tenaculum site on the cervix, making sure to first draw back on the plunger to ensure that the needle is not inserted into a blood vessel.
8. Place tenaculum at the anterior lip of the cervix at 12 o'clock
9. Perform pain scale #2
10. Inject 3 cc of 1% lidocaine and 4 and 8 o'clock position of the cervix. Ensure that you insert the syringe into the cervix at the cervico-vaginal junction and withdraw the plunger to ensure the needle is not inserted into a blood vessel prior to injecting.
11. Wait 3 minutes after last injection before starting IUD insertion procedure
12. Insert IUD
13. Perform pain scale #3
14. Cut IUD strings and remove all instruments from the vagina
15. Perform post procedure vital signs

Paracervical block protocol (Control Arm)

Tools:

Speculum
Single tooth tenaculum

1. Obtain consent and randomization
2. Perform pre-procedure vital signs
3. Insert the speculum into the vagina
4. Perform pain scale #1
5. Identify the cervix
6. Apply Betadine to cervix and surrounding vaginal tissue
7. Place tenaculum at the anterior lip of the cervix at 12 o'clock
8. Perform pain scale #2
9. Insert IUD
10. Perform pain scale #3
11. Cut IUD strings and remove all instruments from the vagina
12. Perform post procedure vital signs

Statistics

Demographic characteristics will be assessed and described using descriptive variables. Vital sign assessment and pain scale assessment will be described using numerical categories. A two tail T-Test will be used to assess the data and we will look for a 20% difference in the pain score.

Ethics

IRB approval will be sought with the University of Texas system.

Informed consent in writing will be obtained in English from each individual prior to enrollment. No coercion will be used. Recruitment and consent will be obtained by [name] and a group of previously authorized and trained residents and attendings working out of the clinic.

Data handling and record keeping

Participant information will be stored on encrypted computers owned by Drs. [name] and [name].

Quality control and assurance

All data collection will be taken by previously authorized members of the aforementioned residency programs.

Publication plan

Results are planned for publication. Participants will not be notified of results.

Sources:

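### Does the loose wording in the summaries leave the timing of the third pain rating unclear?

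*Combined protocol and SAP*

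**What the plan says.** The comparison of interest appears twice. General information: "We will compare the patient's procedural pain level with tenaculum placement and IUD insertion using paracervical block versus no analgesia". Objectives: "We would like to compare patient pain perception in IUD insertion when using paracervical block versus no block".

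Three places describe the third pain rating loosely:

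- Background Information, in the description of the planned trial: "Patient pain will be assessed prior to, during the placement of tenaculum, and after the procedure using the visual analogue scale tool".
- Study Design: pain is "assessed before the procedure but after placement of the speculum, during placement of the tenaculum, and after the procedure".
- Study Design, item g: "Patient rating of pain before, during tenaculum placement, and after the procedure".

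Three places are more exact. The Study Procedures text ties the third rating to placement of the IUD. The study-arm list has insertion at step 12, the third rating at step 13, and string cutting with instrument removal at step 14. The control-arm list has the same three events at steps 9, 10 and 11.

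Vital signs are described in Study Design ("Vital signs will also be taken prior to and after completion of the procedure") and in item f ("Vital signs (including but not limited to blood pressure, respiratory rate, pulse, and oxygen saturation) before and after the procedure"). Study Procedures puts the second set five minutes after the procedure, and both lists put it last.

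**The concern.** If the procedure ends when the instruments come out, the three summary sentences put the third rating later than the step lists do. Items f and g stand next to each other and use the same closing words, so a reader might take pain and vital signs together, minutes after insertion. A score taken then would reflect residual discomfort and not the pain of insertion, which the trial sets out to compare.

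There is a second question: which pain the woman is asked to mark. The second rating is tied to its event, tenaculum placement. The third is only placed after something. She could mark present pain or pain recalled from insertion. If women or staff took this differently, the score would mix two quantities, and this is an open-label trial run at three clinics with rotating residents and faculty.

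The arms also differ between the second rating and insertion. The study arm has two further injection sites and a three-minute wait, and the control arm has neither.

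**Working it through.** There is no planned figure to reproduce, because the point concerns order and wording. The check is a comparison of the texts.

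**Order of events in the two step lists**

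| Event | Study arm step | Control arm step |
|---|---|---|
| Tenaculum placed | 8 | 7 |
| Second pain rating | 9 | 8 |
| Injections at 4 and 8 o'clock, then wait | 10, 11 | none |
| IUD inserted | 12 | 9 |
| Third pain rating | 13 | 10 |
| Strings cut, instruments removed | 14 | 11 |
| Second set of vital signs | 15 | 12 |

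- Insertion to third rating: 13 − 12 = 1 step and 10 − 9 = 1 step.
- Third rating to instrument removal: 14 − 13 = 1 step and 11 − 10 = 1 step.
- Third rating to vital signs: 15 − 13 = 2 steps and 12 − 10 = 2 steps.

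Relative to insertion, the rating has the same position in both arms. The wording conflict therefore creates no scheduled difference between them.

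**Meaning of the word procedure**

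Study-arm step 11 puts the wait before the start of the insertion procedure, so on that use the procedure begins at step 12. Study Procedures places the block ahead of the procedure. Item h of the data list separates complications of the insertion procedure from those of the block. In all three the word means the insertion. A rating at step 13 (or step 10 in the control arm) then does come after the procedure, and the summaries agree with the lists.

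**Link to the vital signs**

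Items f and g share a phrase, but Study Design does not treat the two measures alike: "Vital signs will also be taken prior to and after completion of the procedure" refers to completion, and the pain sentence just before it does not. In Study Procedures the five-minute timing is given for vital signs only, and the next sentence gives the pain rating its own anchor, placement of the IUD. No text puts a pain rating at five minutes.

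**How far apart the readings are**

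If the phrase is taken to mean after the instruments are out, the shift is one step, of unstated length. Scaling the five minutes against the stated maximum subject duration (5/20 = 25%) tells us nothing, because that maximum is defined as "20 minutes or less to place block and insert IUD" and a post-procedure interval lies outside it.

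**Which pain is rated**

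The text is silent on this. The aim in "We will compare the patient's procedural pain level with tenaculum placement and IUD insertion using paracervical block versus no analgesia" names pain with insertion, and the rating is the next step after insertion, with no other step between. Staff who know the aim will ask about insertion. If some women mark present pain instead, the instruction and its timing are still the same in both arms.

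**The case for a change.** The strongest case for a change is that step order fixes when the mark is made but not what it refers to. One sentence would settle that and three phrases could be aligned, with no new visits, staff or patients. Pain scores are the data for the planned t-test, and several operators collect them.

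Part of this stands. The plan does not say whether the rating asks for present or insertion pain, and it uses the word procedure in more than one sense. Tidier wording would do no harm before enrolment.

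The rest is weaker:

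- Injection pain could enter only the study-arm score if a woman marked all pain since the previous rating, but nothing asks her to. The same argument would apply to the second rating, since the study arm has the 12 o'clock injection (step 7) between the first and second ratings and the control arm does not. The longer interval is part of the block being tested.
- How to score a woman in whom no IUD is placed is a real question, but a separate one about incomplete procedures.
- The change is not entirely free. The stated start is October 2016 and this version is dated 01/04/2017. If women were already enrolled, a new instruction could alter what is measured partway through, and earlier and later ratings would have to be told apart.

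**Conclusion.** No change to the plan is needed. The time of the third rating is fixed, and it is the same in both arms: directly after insertion and before the instruments are removed. The looser summary phrase fits that time point on the narrow use of the word procedure found elsewhere in the protocol. The remaining gap, present pain or insertion pain, is one that staff and analysts fill from the stated objective.

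No effect on the between-arm difference has been shown. The documents give no mean or standard deviation of pain, so no size can be derived. The conclusion assumes that operators follow the step lists, which the protocol says are the ones to be used, and that they ask about the pain of insertion. If some women marked present pain, the contrast would be of a slightly different quantity, still measured at the same step in both randomised groups.

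### In an open-label trial, randomization at step 1 makes the only pre-treatment pain and vital-sign values post-allocation, so they are unsafe as baselines

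*Combined protocol and SAP*

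**What the plan says.** Study Design declares the masking: "The study will be an open label randomized controlled trial". The narrative in Study Procedures puts allocation straight after consent: "These women will then be randomized to either a group getting no analgesia during the IUD insertion procedure".

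The study-arm and control-arm lists open with the same five steps:

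1. "Obtain consent and randomization"
2. "Perform pre-procedure vital signs"
3. "Insert the speculum into the vagina"
4. Pain scale #1
5. Identification of the cervix

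Step 6 (Betadine) is also common to both. The arms diverge at step 7.

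Pain scale #1 is described as the pre-procedure rating. Study Design says "The level of pain of each woman will be assessed before the procedure but after placement of the speculum", and Study Procedures says "Patient pain scale will be assessed after speculum placement but prior to any procedure". Vital signs are likewise taken before and after.

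The exclusion criteria in Study Population include "women with current PID, women who are not good candidates for an IUD, and patients who have a Lidocaine allergy". No step says when these are checked. Statistics names a two-tailed t-test and a 20% difference in pain score. It does not say which pain scale is tested, or whether pain #1 or the first vital signs serve as a baseline.

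**The concern.** A baseline in a randomised trial is useful because the arms can differ on it only by chance. That holds if it is measured before allocation, or at least before anyone who could influence it knows the allocation. Here neither is assured. A woman who knows that she will have injections at three sites, or no block, may rate the speculum differently. Her pulse and blood pressure may also respond.

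At stake are three possible uses of these values: before-to-after comparisons of pain or vital signs, a table showing that the arms started equal, and adjustment for pain #1. Adjustment is attractive in a trial of only 50 women because it can gain precision.

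The order has a second effect. Allocation precedes the first view of the cervix, so a woman who withdraws at that stage, or is then found unsuitable, is already a randomised participant. No rule says how she is analysed.

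**Working it through.** **Sequence.** Nothing in the plan disputes the order: the two lists and the narrative agree. That the arm is known from step 1 is an inference. It rests on the open-label design, the separate step and tool lists for each arm, and the absence of any described concealment or delayed disclosure. The protocol does not state when the woman learns her arm.

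**Inputs for an illustration.** From the documents: 50 women, a two-tailed t-test and a 20% difference. Assumed, because the documents give no values:
- 1:1 allocation (25 per arm) and alpha 0.05
- a 100 mm scale with a control mean of about 50 mm, so that 20% is about 10 mm
- an SD of 20-30 mm for the analysed quantity (the change score, or the residual after adjustment)
- no true effect
- a shift of 5 mm in pain #1 in one arm, direction unknown

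The plan has no figure of its own on this point to reproduce.

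**Change score.** The bias equals the shift, 5 mm, which is half of the assumed 10 mm target. The standard error is SD × √(2/25), and the noncentrality is bias ÷ standard error. The two-sided rejection rate comes from the noncentral t with 48 df:

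| SD (mm) | Standard error (mm) | Noncentrality (5 mm) | False-positive rate |
|---|---|---|---|
| 20 | 5.66 | 0.88 | 13.9% |
| 25 | 7.07 | 0.71 | 10.7% |
| 30 | 8.49 | 0.59 | 8.9% |

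**Adjusted analysis.** The bias is slope × shift = 0.4 × 5 = 2 mm. The same calculation gives 6.4%, 5.9% and 5.6% at SD 20, 25 and 30 mm.

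**Sensitivity.** A normal approximation was run with a raw SD of 20-30 mm and a correlation r of 0.3-0.5 between pain #1 and the later score. Here the change-score SD is SD × √(2(1 − r)), the adjusted residual SD is SD × √(1 − r²), and the slope is r.

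| Shift in #1 | Change score | Adjusted |
|---|---|---|
| 5 mm | 8-14% | 5-8% |
| 10 mm | 17-42% | 7-18% |

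**Pain #2 or #3 alone.** Pain #1 does not enter the test statistic, so the rate stays at 5% by this route, before any open-label reporting bias in the outcome itself.

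**Women unsuitable after randomization.** The documents give no rate. The chance of at least one among 50 is 1 − (1 − p)^50, which is 64%, 92% and 99.5% for assumed p of 2%, 5% and 10%. The expected numbers are 1, 2.5 and 5. If these women were dropped, normal-approximation power for an assumed 20 mm difference with SD 25 mm would fall from 81% to 80%, 79% and 77%.

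**The case against.** The strongest reply is that the plan specifies no analysis that this order would bias. General information frames the comparison as pain at tenaculum placement and at insertion, which are scales #2 and #3. Statistics offers a t-test and mentions neither a change score nor adjustment. This stands as a limit on the point: the inflated rates above belong to possible analyses, not to a stated one. It does not remove the point. Statistics leaves the use of pain #1 and the first vital signs open, and collecting vital signs before and after invites a comparison of change.

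A reader might infer more than the documents support, in three ways:

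- **That the main comparison is biased.** A t-test on pain #2 or #3 alone is not, by this route.
- **That the trial has no usable baseline data.** Age, race, gravidity, parity and surgical and infection history are also collected. These are largely fixed facts that knowing the arm cannot change. The problem is confined to pain and vital signs.
- **That women are screened out at the speculum.** No section says IUD candidacy is judged then. Inclusion criteria are met before consent, and age and lidocaine allergy can be checked earlier. Stenosis and failed placement are recorded as complications, not treated as exclusions. The steps up to the view of the cervix are the same in both arms, so anatomical findings should arise equally and mainly cost a little precision. Withdrawal by someone who knows the arm is the part that could differ between arms.

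It is also fair to say that the 5 mm shift is a single assumed value and that randomizing soon after consent is common practice.

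**Conclusion.** The point holds, with limited consequence. The order of steps is certain. Early knowledge of the arm is a reasonable inference that nothing in the documents contradicts. The pre-treatment pain and vital-sign values are therefore post-allocation values in an unblinded trial, and they are unsafe as baselines, as covariates or as evidence of comparability.

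If they were used that way, a 5 mm expectation shift would raise the false-positive rate to about 9-14% for a change score and about 6% for an adjusted analysis. Both figures depend wholly on the assumed scale, SD, slope and shift, and the direction of any bias is unknown. The number of women affected by withdrawal or late unsuitability cannot be estimated from the documents.

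This is a worthwhile, inexpensive improvement. It is not a flaw that invalidates the trial, and it contradicts no stated figure.

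**What to change.** In both step lists, keep consent at step 1 and move allocation to after step 5. The order becomes: consent; history items and prior pain medication; vital signs; speculum; pain scale #1; identification of the cervix; then opening of the allocation (for example a sealed envelope), before the arms diverge at step 7. Placing it directly after pain scale #1 would be too early, because the cervix is identified only at the following step. Amend the Study Procedures narrative to match.

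The cost is one reordered step in two lists, a block tray laid out for all 50 women, and slightly longer with the speculum in place in both arms. The sample size does not change.

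The change protects the baselines and shortens the interval in which a woman or operator who knows the arm could withdraw or switch. It does not remove open-label reporting bias in pain #2 and #3, because the arm is still known when those are scored.

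If the order cannot be changed, Statistics should say that pain #1 and the first vital signs are post-allocation, and that the comparison of pain #2 and #3 uses neither change from them nor adjustment for them.

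### Optional, low-cost gain in precision: parity is collected but has no stated role in the comparison of pain scores, which rests on an unadjusted t-test

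*Combined protocol and SAP*

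**What the plan says.** The front-page summary sets the size at "50 Adults who present for IUD insertion". General information names the comparison as the "procedural pain level with tenaculum placement and IUD insertion", with and without the block.

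The Statistics section is one short paragraph. On inference it says "A two tail T-Test will be used to assess the data" and "we will look for a 20% difference in the pain score". On background variables it says "Demographic characteristics will be assessed and described using descriptive variables". The documents name no regression, stratified analysis, covariate or stratified randomization.

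Item (a) of the data list under Study Design is "Age, race, gravity, and parity". The eligibility criteria do not restrict parity, so it can vary in the sample.

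Study Procedures gives the timing of the pain scores: "Patient pain scale will be assessed after speculum placement but prior to any procedure, with tenaculum placement and after placement of the IUD". In both arms' step lists randomization is step 1 and pain scale #1 is step 4. Study Design states: "The study will be an open label randomized controlled trial".

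**The concern.** In a trial of 50 women the interval for the difference in mean pain will be wide. A baseline variable that explains some of the spread in pain can narrow it without further patients or data. The plan already collects such a candidate and gives it no stated role beyond description. That it will be described and nothing more is an inference from silence, but nothing in the text says otherwise.

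The choice also has to be made in advance. If parity happens to be unevenly split between the arms, an adjustment decided after seeing the split and the pain scores would carry little weight, particularly in an open-label trial.

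The first pain score might seem the more natural covariate. It is less straightforward than parity, because it is recorded after randomization and the documents do not say when the woman learns her arm.

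**Working it through.** **Inputs from the documents.** Total N is 50, the test is a two-sided t-test without covariates, and parity is collected.

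**Assumptions, because the documents give no value.** Allocation 1:1 (n = 25 per arm), two-sided alpha 0.05, 100 mm scale, within-arm SD 25 mm (20 and 30 also tried), no dropout, and parity coded nulliparous/parous with one group making up 50% or 30% of women. The parity gap is the difference in mean pain between the two groups. It is unknown, so 0 to 20 mm is tried.

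**The plan's own figure.** N = 50 cannot be confirmed, because alpha, power, SD and the meaning of 20% are not given. It agrees with 25 per arm if 20% means 20 mm, SD is 25 mm, alpha is 0.05 and power is 80% (80.7% by the normal approximation, 79.1% by the t distribution). That set is used as the base case for illustration. It is not attributed to the plan.

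**Unadjusted.** SE = 25 × √(2/25) = 7.07 mm. With 48 df, t = 2.0106, so the half-width is 2.0106 × 7.071 = 14.22 mm. Noncentral-t power is 79% for a 20 mm difference and 28% for 10 mm.

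**With one covariate.** SE = SD × √[(1 − R²) × (2/n) × (1 + 1/46)] on 47 df (t = 2.0117). The factor 1 + 1/46 allows for chance imbalance of the covariate between the arms. For a binary covariate with proportion p, R² = gap² × p(1 − p) / SD².

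- No relation to pain: SE = 7.071 × √(47/46) = 7.148, and the half-width is 14.38 mm. The ratio 14.38/14.22 = 1.011, so the interval is about 1% wider.
- 20 mm gap, 50:50 mix: R² = 400 × 0.25 / 625 = 0.16, and the half-width is 14.38 × √0.84 = 13.18 mm.

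| Parity mix | Gap (mm) | R² | Half-width (mm) | Power, 20 mm | Power, 10 mm |
|---|---|---|---|---|---|
| Unadjusted | – | – | 14.22 | 79% | 28% |
| Either | 0 | 0 | 14.38 | 78% | 28% |
| 50:50 | 5 | 0.010 | 14.31 | 79% | 28% |
| 50:50 | 10 | 0.040 | 14.09 | 80% | 29% |
| 50:50 | 20 | 0.160 | 13.18 | 85% | 32% |
| 30:70 | 5 | 0.008 | 14.32 | 79% | 28% |
| 30:70 | 10 | 0.034 | 14.14 | 80% | 29% |
| 30:70 | 20 | 0.134 | 13.38 | 84% | 31% |

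**Break-even.** The two half-widths are equal when 1 − R² = (14.217/14.379)², which gives R² = 0.0224. That is a gap of √(0.0224 × 625/0.25) = 7.5 mm at 50:50, or 8.2 mm at 30:70. An interval 5% narrower needs R² of about 0.118, a gap of about 17 mm (50:50) or 19 mm (30:70).

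**Other SDs.** Power for 20 mm with a 20 mm gap at 50:50 goes from 93% to 98% at SD 20 mm, and from 64% to 68% at SD 30 mm.

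**Simulation check.** In 20,000 simulated trials per scenario, the type I error of the parity model stayed near 5%, and power for 20 mm at 50:50 was 78.7%, 80.0% and 85.0% at gaps of 5, 10 and 20 mm. These agree with the formula.

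**The case against.** The strongest reply is that nothing is wrong. An unadjusted t-test is a legitimate choice in a randomized trial. A reader might infer from the missing covariates that the planned analysis is biased or invalid. The documents do not support that, and it is not claimed here.

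Second, nothing in the documents singles out parity. Background Information mentions a trial in nulliparous women but reports no contrast by parity. Age, surgical and infection history, and same-day pain medication are also collected. This stands: choosing parity, and the nulliparous/parous cut, is an assumption.

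Third, the gain is negligible over much of the range. A 5 mm gap makes the interval slightly wider, and a 10 mm gap narrows it by about 1%. It is therefore not true that any covariate related to pain helps; it must explain more than about 2% of the variance. This stands too, and it is why the point is optional.

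A reader might go further on pain scale #1 and infer that it is distorted by knowledge of the arm. The order of steps in an open-label trial means it is not shown to be free of that knowledge, but the documents do not show that it is affected either. No bias is claimed. The order is reason enough to keep #1 out of the main model. A rule admitting it only when the arm had not yet been disclosed could leave the model undefined if disclosure timing varied between women.

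Finally, the stated start is October 2016 and the version date is 01/04/2017, so recruitment may have begun. The documents do not show that any between-arm pain data had been examined, so the timing does not defeat the point.

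**Conclusion.** The point holds as an optional improvement in precision, not as a defect in validity. Under the stated assumptions the downside is an interval about 1% wider (14.38 against 14.22 mm). The upside at a 20 mm parity gap and a 50:50 mix is an interval about 7% narrower (13.18/14.22 = 0.927) and about 6 points more power for a 20 mm difference. Which of these applies depends on a relation between parity and pain that the documents do not give.

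A reader might hope that adjustment would secure the trial's power. It would not. For a true difference of about 10 mm, power stays between 28% and 32% across the gaps tried at SD 25 mm. Nor does adjustment supply the missing SD, alpha or definition of the 20% difference.

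**What to change.** In the Statistics section, before any between-arm look at the pain data:

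- Pre-specify, for the raw pain scores #2 (tenaculum) and #3 (IUD insertion), a linear model with arm and parity, coded nulliparous or parous.
- Report the adjusted difference between arms with its 95% confidence interval, and the unadjusted two-sample t-test alongside it.
- State that pain scale #1 is not in the main model and is used only in a sensitivity analysis.

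The cost is wording. No new data, patients or procedures are needed, and the main model uses one of the 48 degrees of freedom. The risk is no gain, or the interval about 1% wider, if parity is weakly related or unrelated to pain. If #1 is added to parity in the sensitivity analysis and neither predicts pain, the half-width there is about 14.55 mm (14.55/14.22 = 1.023, about 2.3% wider). Naming a primary score and handling two comparisons are separate matters that this change does not settle.
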